13      Institutional research policies and procedures.

14        **1.1 Specific Aims and Hypothesis**

15        The primary aim of this study is to compare the 30 and 90-day overall/cumulative grade III or  
16        higher complication rates between patients with severe obstructive jaundice undergoing  
17        preoperative endoscopic biliary drainage with SEMS and patients undergoing direct surgical  
18        resection. In this study, **One arm undergoes preoperative biliary drainage followed by surgery and**  
19        **the other arm undergoes surgical resection** without prior biliary drainage. Secondary aims will be  
20        to compare surgical outcomes including mortality, intra-operative parameters, hospital length of  
21        stay, ICU length of stay, readmission rate and time to commencement of adjuvant treatment.

22        **1.2 Background and Rationale**

23        Despite the fact that endoscopic and percutaneous placement of biliary stents is technically  
24        successful in 90-95% of cases, routine preoperative biliary drainage for pancreatic cancer remains  
25        controversial.[4, 5] Pooled data from retrospective studies published over the past several years  
26        have shown similar rates of 30-day mortality after pancreaticoduodenectomy in those who have  
27        undergone biliary decompression as compared to those who have not. A few studies have  
28        suggested that routine preoperative drainage in patients undergoing surgery for cancer of the  
29        pancreatic head may increase overall complications, likely due to complication related to the  
30        endoscopy itself (i.e. pancreatitis, bleeding, perforation) and complications related to stent  
31        failure.[6] In the largest, multicenter, randomized trial to date, patients were randomly assigned  
32        to undergo either endoscopic preoperative biliary drainage for 4 to 6 weeks, followed by surgery,  
33        or surgery alone after diagnosis. In this study, endoscopic preoperative biliary drainage did not  
34        have a beneficial effect on the surgical outcome but rather was associated with an increase in  
35        serious complications.[7]

36  
37        On the other hand, outcome measures have not been standardized and the lack of complete data  
38        on surgical complications following preoperative drainage make direct comparisons difficult and  

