65 obstruction prior to surgery. This represents the first biliary metal stent with labeling to support  
66 pre-operative drainage in the US.

67 **1.4 Preclinical Data**

68 Please see clinical data below

69 **1.5 Clinical Data to Date**

70 A recent meta-analysis of 1989 patients showed that SEMS have higher stent insertion success,  
71 lower risk of stent occlusion, lower re-intervention rate, fewer therapeutic failures, and fewer  
72 episodes of cholangitis compared to plastic stents making them the optimal choice for biliary  
73 decompression.[8] Also a recent randomized controlled trial confirmed that SEMS are superior to  
74 plastic stents with regard to functional stent time and showed that the total health care cost is  
75 similar for placing SEMS or plastic stents even in patients with survival less than 3 months

76 **1.6 Dose Rationale and Risk/Benefits**

77 The study doesn't involve drug administration.

78 **2.0 STUDY OBJECTIVES**

79 **2.1 Primary Objective:**

80 The primary aim of this study is to compare the 30 and 90-day overall complication rates between  
81 patients with severe obstructive jaundice undergoing preoperative endoscopic biliary drainage  
82 with SEMS and patients undergoing direct surgical resection.

83 **2.2 Secondary Objective:**

84 Secondary aims will be to compare surgical outcomes including hospital length of stay, ICU  
85 length of stay, readmission rate, disposition from hospital, emergency room visits, urgent care  
86 center visits and time to commencement of adjuvant treatment.

87 **3.0 STUDY DESIGN**

88 **3.1 General Design**

89 This is a Randomized controlled trial.

92 ERCP will be performed on those who are randomized to the intervention group with 24 hours of  
93 randomization. The patient will be followed at 30 days and 90 days post-operatively.

94 **3.2 Primary Study Endpoints**

95 30 and 90 day- complication rates between patients with severe obstructive jaundice undergoing  
96 preoperative endoscopic biliary drainage with SEMS and patients undergoing direct surgical  
97 resection

98 **3.3 Secondary Study Endpoints**

99 Secondary aims include the total number of complications, intraoperative estimated blood loss,  
100 number of required fluid boluses, postoperative hospital LOS, readmission rate, disposition from  
101 hospital, time to commencement of adjuvant treatment, emergency room visits, urgent care center  

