139 4.5 Early Withdrawal of Subjects

140 **4.5.1 When and How to Withdraw Subjects**

141 Patients can withdraw from the study at any time. Stent placement is the standard of care and thus  
142 subjects who elect to withdraw from the study will continue to have the biliary stent in place and  
143 be followed regularly similar to patients that are enrolled in the study.

144 **4.5.2 Data Collection and Follow-up for Withdrawn Subjects**

145 Subjects who elect to withdraw from the study will continue to be followed on a regular basis.  
146 Data that is important to the integrity of the final study analysis and the safety profile of the  
147 SEMS will be collected after obtaining approval of the subjects.

148

149 **5.0 STUDY DRUG/THERAPY**

150 5.1 Description

151 The stents to be used in this study are FDA approved WallFlex Biliary RX Stents (Boston  
152 Scientific Corporation, Natick, MA, USA) which are available in diameters of 8 or 10 mm and  
153 lengths of 40, 60, and 80 mm.

154 5.2 Treatment Regimen

155 Stent to be placed pre-operatively in the intervention group to be removed during surgery.

156 5.3 Risks

• Pain	• Infection	• Tumor overgrowth around ends of stent
• Bleeding	• Inflammation	• Mucosal hyperplasia
• Fever	• Recurrent obstructive jaundice 26% (likely)	• Cholangitis
• Nausea	• Stent occlusion	• Cholecystitis 10% (likely)
• Vomiting	• Tumor ingrowth through the stent	• Pancreatitis 6% (possible)
• Bile duct ulceration	• Perforation of duodenum or bile duct	• Stent migration 8% (possible)
• Perforation of the gall bladder due to the stent covering the cystic duct	• Stent misplacement	

157

158

159 Once again, placement of SEMS is the standard of care for patient with profound jaundice despite  
160 the lack of evidence to support this practice.

161 5.4 Method for Assigning Subjects to Treatment Groups  
162 A randomization schedule will be created by the study statistician using the method of random  
163 permuted blocks. Randomization assignments will be loaded into a REDCap database before  
164 study enrollment begins. Randomization assignments will be accessed through the REDCap  
165 randomization facility.

166 5.5 Preparation and Administration of Study Drug/Therapy  
167 The intervention group will receive a WallFlex Biliary RX Stents (Boston Scientific Corporation,  
168 Natick, MA, USA)

169 5.6 Subject Compliance Monitoring  

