- 308           • Hospitalization or prolonged hospitalization required to allow efficacy  
 309           measurement for the study.
- 310           • Hospitalization or prolonged hospitalization for therapy of the target disease of the  
 311           study, unless it is a worsening or increase in frequency of hospital admissions as  
 312           judged by the clinical investigator.

313           8.2 Recording of Adverse Events

314           At each contact with the subject, the investigator must seek information on adverse events by  
 315           specific questioning and, as appropriate, by examination. Information on all adverse events  
 316           should be recorded immediately in the source document, and also in the appropriate adverse event  
 317           module of the case report form (CRF). All clearly related signs, symptoms, and abnormal  
 318           diagnostic procedures results should be recorded in the source document, though should be  
 319           grouped under one diagnosis.

320           All adverse events occurring during the study period must be recorded according to the following:

Adverse event	Start date	SAE* 1. Yes (also complete SAE form) 2. No	Causality 1. Unrelated 2. Possibly Related	Severity 1. Mild 2. Moderate 3. Severe	Expectedness 1. Expected 2. Unexpected	DATE of assessment and INITIALS of delegated clinician	Outcome 1. Resolved 2. Ongoing	Date Resolved	AE Recorded by (initials)

324  
325  
326 The clinical course of each event should be followed until resolution, stabilization, or until it has  
327 been determined that the study treatment or participation is not the cause. Serious adverse events  
328 that are still ongoing at the end of the study period must be followed up to determine the final  
329 outcome. Any serious adverse event that occurs after the study period and is considered to be  
330 possibly related to the study treatment or study participation should be recorded and reported  
331 immediately.

332 **8.4 Stopping Rules**

333 We will do an interim analysis after reaching 50 patients, and if there is a significant  
334 difference (> 20%) in post operative mortality or morbidity in one group versus the other,  
335 then the study will be discontinued.

336 **8.5 Data and Safety Monitoring Plan**

337 It is the responsibility of the Principal Investigator to oversee the safety of the study at his/her  

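### The only mandatory stopping rule (Section 8.4), as naturally read, leaves out serious events and deaths between randomisation and resection

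*Combined protocol and SAP*

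**What the plan says.** Section 8.4 (Stopping Rules) sets a single look: "We will do an interim analysis after reaching 50 patients, and if there is a significant" "difference (> 20%) in post operative mortality or morbidity in one group versus the other", "then the study will be discontinued". It is the only stopping criterion in the protocol with a threshold and a required consequence, and it acts in either direction.

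The arms differ before surgery. Section 3.1 says "ERCP will be performed on those who are randomized to the intervention group with 24 hours of" randomisation. Section 5.2 adds "Stent to be placed pre-operatively in the intervention group to be removed during surgery". Section 1.2 reports that a few earlier studies suggested more complications with routine drainage, and gives as the likely cause complications of the "endoscopy itself (i.e. pancreatitis, bleeding, perforation) and complications related to stent" failure. Section 5.3 lists stent risks, among them pancreatitis at 6% and cholecystitis at 10%, without severity or time window.

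Other sections cover the pre-operative period. Adverse events are reportable from randomisation to 90 days after surgery (Section 8.1). The Medical Monitor may recommend suspension or termination (Section 8.5.1). The DSMC votes on study status (Section 8.5.2). The IRB may suspend or terminate (Section 10.2.1). None of these routes has a numeric criterion.

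**The concern.** The rule starts its count at surgery, but the treatments diverge at randomisation. A patient who dies of post-ERCP pancreatitis before resection adds nothing to the comparison that decides whether the trial must stop. Stent harms that appear or persist after surgery do count; those confined to the drainage period do not.

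If drainage adds serious pre-operative events beyond those in controls, two things follow. The mandatory stop is less likely to fire for harm than a count from randomisation would be. It is also more likely to end the trial for apparent stent benefit, because the cost of obtaining that benefit is left out. The discretionary routes can stop the trial for pre-operative harm, but nothing in Section 8.5 holds back a mandatory stop in favour of stenting.

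**Working it through.** **The plan's own figures.** Section 8.4 states no operating characteristics. The Section 7.1 power reproduces with a pooled one-sided normal approximation (83.4%, 65.7% and 44.9%, against the stated 84%, 66% and 44%), but the point does not depend on it.

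**Inputs.**
- 25 per arm: half of the 50 patients in Section 8.4, assuming near-equal allocation at the look.
- Threshold: more than 20% read as absolute points, an assumption. Since 0.20 × 25 = 5, the rule fires at 6 or more excess events.
- Control post-operative rate 50%. Section 7.1 gives 50% as an overall grade III or higher rate; using it as a post-operative rate is an assumption.
- Stent post-operative rate: 50% (no effect), or 25% and 35% (alternatives in Section 7.1).
- Stent serious pre-operative rate r: 6% and 10%, assumed. They match two figures in Section 5.3, but the documents give no overall serious pre-operative rate.
- Complete follow-up, independence, and no control pre-operative events.

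**Formula.** Stent rate from randomisation = 1 − (1 − post)(1 − r). With post = 0.50 and r = 0.06: 1 − 0.50 × 0.94 = 0.530. The probability of stopping is the sum of the products of the two binomial(25) probabilities over all pairs of counts that differ by 6 or more in the stated direction.

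| Stop | Stent post-op rate | As written | From randomisation, r = 6% | From randomisation, r = 10% |
|---|---|---|---|---|
| Harm | 50% | 5.9% | 8.9% (stent rate 53.0%) | 11.4% (55.0%) |
| Benefit | 25% | 59.4% | 46.0% (29.5%) | 37.4% (32.5%) |
| Benefit | 35% | 30.8% | 21.8% (38.9%) | 16.8% (41.5%) |

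**Sensitivity.** Each cell shows as written, then r = 6% and r = 10%.

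| Change in assumption | Harm | Benefit, 25% | Benefit, 35% |
|---|---|---|---|
| Two-sided p < 0.05 (pooled z) also required | 3.3%; 5%, 7% | 48%; 35%, 27% | 21%; 14%, 11% |
| Pre-operative event raises post-operative risk 1.5-fold, marginal rate fixed | 5.9%; 7%, 8% | 59%; 48%, 41% | 31%; 24%, 20% |
| 10% pre-operative events in controls (control rate 55%) | 5.9%; 4%, 6% | 59%; 61%, 52% | 31%; 34%, 27% |

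In the second row, stent rate = r + post − 1.5 × r × post. In the third, control rate = 1 − 0.50 × 0.90 = 0.55.

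Two further readings of Section 8.4 change the levels. If morbidity means any grade, with an assumed 70% in both arms, the harm stop is 4.4% as written against 5.7% and 6.7%. If 20% is relative (ratio above 1.2 or below 0.8), the as-written stops are 25% for harm and 89% and 65% for benefit; the direction of the gap is unchanged.

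**Is the benefit real in these cases?** With no control pre-operative events, stenting stops being better overall when r reaches 1 − 0.5/(1 − post): 33.3% at a post-operative rate of 25%, and 23.1% at 35%. At r of 6% or 10% the stent rates of 29.5% to 41.5% all stay below 50%.

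**The case against.** The strongest reply is that oversight already covers these events. The Medical Monitor reviews reportable events in real time and can trigger an ad hoc DSMC meeting. These routes run from the first patient, whereas Section 8.4 is one look at 50. For early ERCP harm they are the faster safeguard. That stands: a reader might infer that pre-operative harm goes unmonitored, and Sections 8.1 and 8.5 show otherwise. What remains is that those routes are discretionary and do not put pre-operative events into the mandatory comparison.

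A second reply is that *post operative* might qualify only *mortality*, leaving morbidity open in time. That reading is strained, and pre-operative deaths would still be excluded.

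A third is that the effect is small and rests on assumptions. That stands too. At 6% to 10% the harm stop moves by 3 to 5 points. With 10% pre-operative events in controls, the harm gap is near zero at r = 10%, and all three comparisons reverse at r = 6%. Such control events are plausible in patients with bilirubin above 10 mg/dL. It might be tempting to add up the Section 5.3 risks and assume serious pre-operative rates of 20% or 30%, where the gap would be large. The documents do not support this, because those figures carry no severity or timing.

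Finally, a reader might infer that the rule would stop the trial for a false benefit. In the cases shown, stenting is still better overall, but by less than the rule sees.

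**Conclusion.** The point holds as a gap in the event window of Section 8.4. The only mandatory stopping criterion, as naturally read, leaves out events and deaths before resection, in a trial where only one arm has an added procedure then. In the base illustration the harm stop is 5.9% instead of 9% to 11%. The benefit stop is 59% instead of 37% to 46%, or 31% instead of 17% to 22%, depending on the stent post-operative rate. These figures are not estimates. They rest on the absolute reading of 20%, the assumed 50% post-operative control rate, the assumed pre-operative rates, independence and no control pre-operative events.

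The case for change does not depend on one scenario: a stopping comparison between randomised arms should count both from randomisation. Given the existing oversight and the modest size, this is an inexpensive improvement. It does not show that participants are unprotected.

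**What to change.** In Section 8.4, replace the post-operative event set with: *mortality or morbidity from randomisation through post-operative follow-up, in all randomised patients as randomised, including ERCP-, stent- and obstruction-related events before surgery*. Keep the post-operative comparison as a supporting display for the DSMC.

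Apply the rule to the first 50 randomised patients over the same follow-up in both arms, for example to 30 days after surgery. For patients never resected, use a fixed time from randomisation chosen by the sponsor. A simple data cut would mislead, because stent patients reach surgery later. With equal 50% post-operative rates, r = 10%, all controls operated on but only 80% of stent patients, the observed stent rate is 0.10 + 0.90 × 0.80 × 0.50 = 0.46. The benefit stop is then 10.1% and the harm stop 3.3%.

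Restricting morbidity to grade III or higher, or waiting for the full 90 days, is optional and not needed to close the gap.

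The cost is a few sentences, since events are already collected from randomisation. Pre-operative events must be graded consistently with post-operative ones: the Section 8.2 log has mild, moderate and severe, while Section 8.5.1 refers to CTC 4.0. The look may come slightly later, though the rule as written also needs some post-operative follow-up. The rule may also fire somewhat more often against stenting.

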## 403       9.0 DATA HANDLING AND RECORD KEEPING

### 404       9.1 Confidentiality

405       Information about study subjects will be kept confidential and managed according to the  
406       requirements of the Health Insurance Portability and Accountability Act of 1996 (HIPAA).  
407       Those regulations require a signed subject authorization informing the subject of the following:

408       • What protected health information (PHI) will be collected from subjects in this study  
409       • Who will have access to that information and why  
410       • Who will use or disclose that information  
411       • The rights of a research subject to revoke their authorization for use of their PHI.

412       In the event that a subject revokes authorization to collect or use PHI, the investigator, by  
413       regulation, retains the ability to use all information collected prior to the revocation of subject  
414       authorization. For subjects that have revoked authorization to collect or use PHI, attempts should  
415       be made to obtain permission to collect at least vital status (i.e. that the subject is alive) at the end  
416       of their scheduled study period.

417

418 9.2 Source Documents

419 Source data is all information, original records of clinical findings, observations, or other  
420 activities in a clinical trial necessary for the reconstruction and evaluation of the trial. Source  
421 data are contained in source documents Examples of these original documents, and data records  
422 include: hospital records, clinical and office charts, laboratory notes, memoranda, subjects'  
423 diaries or evaluation checklists, pharmacy dispensing records, recorded data from automated  
424 instruments, copies or transcriptions certified after verification as being accurate and complete,  
425 microfiches, photographic negatives, microfilm or magnetic media, x-rays, subject files, and  
426 records kept at the pharmacy, at the laboratories, and at medico-technical departments involved in  
427 the clinical trial.

428 9.3 Case Report Forms

429 The study case report form (CRF) is the primary data collection instrument for the study. All data  
430 requested on the CRF must be recorded. All missing data must be explained. If a space on the  
431 CRF is left blank because the procedure was not done or the question was not asked, write "N/D".  
432 If the item is not applicable to the individual case, write "N/A". All entries should be printed  
433 legibly in black ink. If any entry error has been made, to correct such an error, draw a single  
434 straight line through the incorrect entry and enter the correct data above it. All such changes must  
435 be initialed and dated. DO NOT ERASE OR WHITE OUT ERRORS. For clarification of  
436 illegible or uncertain entries, print the clarification above the item, then initial and date it.  
437

438 *Please refer to CRF in the Appendix*

439 9.4 Records Retention

440 It is the investigator's responsibility to retain study essential documents for at least 2 years after  
441 the last approval of a marketing application in their country and until there are no pending or  
442 contemplated marketing applications in their country or at least 2 years have elapsed since the  
443 formal discontinuation of clinical development of the investigational product. These documents  
444 should be retained for a longer period if required by an agreement with the sponsor. In such an  
445 instance, it is the responsibility of the sponsor to inform the investigator/institution as to when  
446 these documents no longer need to be retained.  
447

448 10.0 STUDY MONITORING, AUDITING, AND INSPECTING

449 10.1 Study Monitoring Plan

450 The investigator will allocate adequate time for monitoring activities. The Investigator will also  
451 ensure that the medical monitor or other compliance or quality assurance reviewer is given access  
452 to all the above noted study-related

453 documents and study related facilities (e.g. pharmacy, diagnostic laboratory, etc.), and has  
454 adequate space to conduct the monitoring visit.

455 10.2 Auditing and Inspecting

456 The investigator will permit study-related monitoring, audits, and inspections by the IRB, the  
457 funding sponsor, government regulatory bodies, and University compliance and quality assurance  
458 groups of all study related documents (e.g. source documents, regulatory documents, data

459 collection instruments, study data etc.). The investigator will ensure the capability for inspections  
460 of applicable study-related facilities (e.g. pharmacy, diagnostic laboratory, etc.).

461  
462 Participation as an investigator in this study implies acceptance of potential inspection by  
463 government regulatory authorities and applicable University compliance and quality assurance  
464 offices.

465

466 **10.2.1 Independent External and Internal Audits**

467 In addition to review by the DSMC, all studies initiated by KCC investigators are audited by an  
468 independent auditor once they have achieved 10% of target accrual. However, a study can be  
469 audited at any time based on recommendations by the IRB, DSMC, CCRRC and/or the Director  
470 of Clinical Investigations, KCC. Studies are re-audited once they have achieved 50% of target  
471 accrual. Special audits may be recommended by the IRB, DSMC or CCRRC based on prior  
472 findings, allegations of scientific misconduct and where significant irregularities are found  
473 through quality control procedures. Any irregularities identified as part of this process would  
474 result in a full audit of that study.

475

476 In addition to the audits at 10 and 50%, the CRMO randomly audits at least 10 percent of all  
477 patients entered into therapeutic KCC trials and other trials as necessary, on at least a bi-annual  
478 basis, to verify that there is a signed and dated patient consent form, the patient has met the  
479 eligibility criteria, and that SAEs are documented and reported to the TJU IRB.

480

481 All audit reports are submitted to the DSMC for review and action (when appropriate). A copy of  
482 this report and recommended DSMC action is sent to the CCRRC and TJU IRB. The committee  
483 regards the scientific review process as dynamic and constructive rather than punitive. The review  
484 process is designed to assist Principal Investigators in ensuring the safety of study subjects and  
485 the adequacy and accuracy of any data generated. The TJU IRB may, based on the DSMC and  
486 auditor's recommendation, suspend or terminate the trial.

487

488 **Coordinating Site Study Team**

489 Representatives from the Thomas Jefferson University Study Team will monitor on site at the  
490 participating site (or virtually if geographically impossible) within 4 weeks of the first subject  
491 enrolling.

492

493 Additional study monitoring by an independent auditing agency will be conducted at 10% and  
494 50% site accrual per the TJU Data and Safety Monitoring Plan. This will either occur on-site, if  
495 feasible, or will require participating sites to send TJU all source documents, patient charts, etc. to  
496 TJU for the audit.

497

498 **Study Team Conference Calls**

499 Teleconferences with the PIs, research nurses/coordinators, and regulatory staff will occur  
500 quarterly. This will be a forum to discuss study related issues including accrual, SAE/AEs  
501 experienced, study response, deviations/violations and study management issues. Minutes of  
502 these discussions will be taken to document the date of these meetings, the participants and the  
503 issues that were discussed. Copies of these minutes will be maintained in the Regulatory Binders  
504 at both sites.

505

506 **11.0 ETHICAL CONSIDERATIONS**

507 This study is to be conducted according to US and international standards of Good Clinical  
508 Practice (FDA Title 21 part 312 and International Conference on Harmonization guidelines),  
509 applicable government regulations and Institutional research policies and procedures.

510  
511 This protocol and any amendments will be submitted to a properly constituted independent  
512 Institutional Review Board (IRB), in agreement with local legal prescriptions, for formal approval  
513 of the study conduct. The decision of the IRB concerning the conduct of the study will be made  
514 in writing to the investigator before commencement of this study.

515  
516 All subjects for this study will be provided a consent form that is compliant with local and federal  
517 regulations, describing this study and providing sufficient information for subjects to make an  
518 informed decision about their participation in this study. See Attachment for a copy of the  
519 Subject Informed Consent Form. This consent form will be submitted with the protocol for  
520 review and approval by the IRB for the study. The formal consent of a subject, using the IRB-  
521 approved consent form, must be obtained before that subject is submitted to any study procedure.  
522 This consent form must be signed by the subject or legally acceptable surrogate, and the  
523 investigator-designated research professional obtaining the consent.

524

525 **12.0 STUDY FINANCES**

526 **12.1 Funding Source**

527 This is an unfunded study. The protocol prospectively tracks standard clinical care. It will be  
528 supported by the investigators, fellows, residents, and research coordinators in the Department of  
529 Surgery and the Division of Gastroenterology. There are no additional costs to the study

530

531 **12.2 Conflict of Interest**

532 Any investigator who has a conflict of interest with this study (patent ownership, royalties, or  
